This study will follow a design and methodology similar to what was done in the initial study, albeit adapted to the age range of the child sample. There will be some differences, however. The proposed study will not incorporate fMRI methods as was done in the initial trial. Instead, the focus will be on examining clinical outcomes based strictly on a broad range of standardized cognitive and neurobehavioral measures. That is intended not only to streamline the cost of the proposed study; it also will allow subject selection to be less restrictive. A number of otherwise suitable cases had to be excluded in the previous trial due to failing to meet criteria specifically having to do with the MRI scanning (e.g., no metal objects or implanted devices, claustrophobia, etc.). More generally, it was felt that there would be fewer potential problems with the participation or compliance of children if fMRI scans were not involved.

Also, unlike the initial trial, subject selection will not be restricted to only those with moderate-severe TBI. It will be extended to also include cases with milder TBI who have documented persistence in cognitive changes, including impaired attention. That would encompass many common cases of TBI, and greatly broaden the potential pool. Even if the attention deficits in these cases would not prove to be chronic, helping to enhance functioning in the earlier stages of recovery can have a beneficial effect on overall outcomes and limit secondary problems that might otherwise arise. Lastly, the interval from the time of injury to when a case is eligible for inclusion in the study will be reduced from 6 months to 2 months. This is intended to capture the child subjects earlier on in the recovery process. It will help reduce the attrition of potential cases who otherwise might be lost to follow-up or who wind up getting started on other treatments. Regardless of the exact point within the eligible time interval post-injury, it will be necessary that each case be judged to be neurologically stable but having persistent attention deficits.

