- Conners-3 Parent and Self-Report Forms (ratings of ADHD symptoms and related areas)*

- Child Behavior Checklist (parent ratings of more general behavioral and emotional problems)
- Children’s Depression Inventory-2 (self-report of depression symptoms)
- Children’s Manifest Anxiety Scale-2 (self-report of anxiety symptoms)
- Behavior Rating Inventory of Executive Function (BRIEF) - Parent Report Form (also Self-Report Form for cases 11 years and older)

* Short-forms of the Conners-3 will be obtained during weekly visits with the project nurse

Note. The above will provide a broad-based assessment of cognition and behavioral/emotional status, as well as focusing especially on attention-related areas. It incorporates measures assessing the four components in Musky’s model of attention: *focus-execute*, *sustain*, *encode*, and *shift*.⁹

Classification of TBI Pattern and Severity

Brain injury measures will be based on medical record information (including head CT findings, Glasgow Coma Scale ratings, etc.) obtained during the medical care immediately following TBI. Subsequent clinical findings, when available, will be taken into consideration as well as information having to do with post-injury mental status obtained in the screening visit with potential candidates.

Conventional score ranges on the Glasgow Coma Scale (GCS) will be used in differentiating three levels of TBI severity: Cases with GCS scores of 13-15 will be rated as having mild TBI; those with scores of 9-12 will be rated as moderate; and those with scores of 8 and lower will be rated as severe. Next, these designations will be considered together with head CT findings. Any case rated as mild based on the GCS score alone should be re-characterized as moderate if there is evidence of an intracranial brain injury documented by CT. Conversely, any case rated as severe based on the GCS score should be upgraded to moderate in the absence of CT scan evidence of an intracranial injury. In addition, there has to be other evidence supporting an impression of a TBI of at least moderate severity, such as the presence of posttraumatic amnesia of 3 days or more not judged to be due simply to confounding factors such as sedation effects. The same is so for any case with a GCS score rated as moderate but who lacked CT evidence of intracranial injury. Taken together, these rules will be used in defining a Composite Index of TBI Severity.

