Cases will also be distinguished based on whether there are indications of white matter injury evident on CT. Cases with/without CT indications of frontal lobe injury will be differentiated as well. These determinations, as well as the final severity ratings, will be made with the input of a physician with a specialty in the diagnosis and management of TBI in children.

Data Analyses

The double blind, crossover design allows for the assessment of both within-subjects and between subjects contrasts. The primary analyses will consist of multiple paired-samples t-tests comparing LDX versus placebo on each of the neurobehavioral dependent measures in the study.

No formal correction for multiple comparisons will be applied so as to not limit sensitivity in detecting possible treatment effects. A p value equal to, or less than, 0.05 will be considered statistically significant. All tests will be two-tailed. All analyses will be performed using Statistical Programs for the Social Sciences (SPSS for Windows, Version 21.0, IBM Corp, 2012).

Possible order effects (depending on whether drug treatment comes before or after placebo) will be examined through a separate analysis of variance (ANOVA) for each dependent measure using a two-factor model (treatment, order, and treatment x order interaction).

There will also be applications of analysis of covariance (ANCOVA) to determine possible mediating or moderating effects of certain pre-treatment variables on treatment outcomes (demographics, brain injury variables, IQ and other cognitive factors, motor control integrity, behavioral symptom profiles and personality features). We anticipate that the distribution of cases in terms of TBI severity will permit an analysis of comparative treatment outcomes for children with mild versus moderate versus severe brain injuries.

Also, safety data will be examined carefully based on weekly visits over the course of the trial. Comparisons will be made on LDX versus placebo for indices such as blood pressure and heart rate, side effects (insomnia, decreased appetite or weight loss, etc.) or significant adverse events, if any.

Safety Monitoring

Because this is a clinical trial of an FDA-approved medication with a favorable safety profile, there will be no independent data safety monitoring board (DSMB) or Safety Officer for this study. Patient safety will be monitored using best practice clinical care standards.

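### Do the gaps in the injury-severity rule, and its overlap with CT location, undermine the planned moderator analyses?

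*Combined protocol and SAP*

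**What the plan says.** Under Classification of TBI Pattern and Severity, each child is first placed by Glasgow Coma Scale: 13–15 mild, 9–12 moderate, 8 or lower severe. CT then modifies the level. A mild case "should be re-characterized as moderate if there is evidence of an intracranial brain injury documented by CT". In the other direction, "any case rated as severe based on the GCS score should be upgraded to moderate in the absence of CT scan evidence". A further condition follows: "there has to be other evidence supporting an impression of a TBI of at least moderate severity", with post-traumatic amnesia of at least 3 days as an example. It is extended: "The same is so for any case with a GCS score rated as moderate but who lacked CT evidence of intracranial injury". The result is a composite severity index.

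The same section derives two more injury variables from CT: "Cases will also be distinguished based on whether there are indications of white matter injury evident on CT", and "Cases with/without CT indications of frontal lobe injury will be differentiated as well". A physician specialising in pediatric TBI contributes to these determinations and to the final severity ratings.

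The Introduction says that "subject selection will not be restricted to only those with moderate-severe TBI", and the inclusion criteria admit all three levels. Data Analyses plans "analysis of covariance (ANCOVA) to determine possible mediating or moderating effects of certain pre-treatment variables on treatment outcomes". Its list of variables covers brain injury, IQ, motor control, behavioral symptoms and personality, among others. It also anticipates a three-way comparison by severity. The sample is about 20 children.

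**The concern.** Three things look wrong.

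- **A level is missing.** A CT-negative child with GCS 12 or lower needs other evidence of at least moderate injury, and the text does not say what happens without it. Such a child is eligible, so membership of the severity groups seems to depend on an unstated choice.
- **Severity and CT location are tied by construction.** A child rated mild cannot have frontal or white-matter injury on CT, and a child rated severe must have some CT injury. If severity alone changes response to LDX, a with/without comparison on location picks up part of that effect, and the reverse holds too. Benefit could be credited to the wrong injury feature.
- **Wording.** No listed instrument is described as a personality measure. A pre-treatment variable can moderate a treatment effect but cannot mediate it.

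The stakes are real in principle. The Introduction names pattern and severity of injury first among the moderators, and severity has its own planned comparison. Results are judged at p ≤ 0.05 with no multiplicity correction.

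**Working it through.** The plan gives no severity split, CT-positive share or expected moderator effect, so there is no figure of its own to reproduce. Units below are SDs of a child's LDX-minus-placebo difference. All splits (mild/moderate/severe) are assumptions for 20 children.

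**1. What the rule assigns.** Three GCS bands × CT × other evidence make 12 profiles.

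| GCS | CT-positive | CT-negative, other evidence | CT-negative, none |
|---|---|---|---|
| 13–15 | moderate | mild | mild |
| 9–12 | moderate | moderate | not stated |
| ≤ 8 | severe | moderate | not stated |

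Each CT-positive cell covers two profiles, so 10 of 12 have a level and 2 do not. If 5%, 10% or 20% of children fell in the gap, the chance of at least one in 20 is 1 − 0.95²⁰ = 64%, 1 − 0.90²⁰ = 88% or 1 − 0.80²⁰ = 99%.

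**2. What the missing level could move.** Let k unassigned children join a mild group of size a, or a moderate group of size b, with no true severity effect. Take k = 1 to 4 and a/b = 7/6, 6/6, 6/6, 6/5.

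- Mild versus not rated: the SD of the shift in the mild–moderate contrast is √[1/a − 1/(a+k)], which gives 0.13 to 0.26.
- Mild versus moderate: the variance is [1/a − 1/(a+k)] + [1/b − 1/(b+k)] + 2k/[(a+k)(b+k)]. For k = 4 this is 0.067 + 0.089 + 0.089 = 0.244, SD 0.49; for k = 1 the SD is 0.28.

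These shifts are noise around zero, not bias. For comparison, the 95% half-width of the mild–severe contrast is t(0.975, 16) × √(1/n₁ + 1/n₃). It is 2.12 × √(1/8 + 1/6) = 1.14 at 8/6/6 and 2.12 × √(1/5 + 1/3) = 1.55 at 5/12/3.

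**3. How large a false location effect could be.** Assume mean responses of 0/0.5/1.0 by severity, no true location effect, 50–100% of moderate cases CT-positive, and the location present in 30–70% of CT-positive cases. The false effect is mean(with) − mean(without). Example at 10/6/4 with shares 0.75 and 0.5:

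- With: 6 × 0.75 × 0.5 = 2.25 moderate and 4 × 0.5 = 2 severe; mean (2.25 × 0.5 + 2 × 1)/4.25 = 0.735.
- Without: 10 mild, 3.75 moderate, 2 severe; mean (3.75 × 0.5 + 2 × 1)/15.75 = 0.246.
- Difference: 0.49.

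The range is over all shares. Test results come from simulations with treatment sequence fitted, at 2,000–3,000 replicates per setting; runs with fewer than two location-positive children were set aside.

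| Split | False effect | Unadjusted false-positive rate | Severity-adjusted 95% half-width | Runs set aside, up to |
|---|---|---|---|---|
| 7/7/6 | 0.32–0.51 | 7–16% | 1.3–1.6 | 18% |
| 10/6/4 | 0.41–0.58 | 8–17% | 1.5–1.7 | 33% |
| 12/5/3 | 0.47–0.62 | 9–19% | 1.77–1.86 | 50% |
| 5/12/3 | 0.19–0.32 | 4–9% | 1.26–1.49 | 21% |

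With severity in the model, the false-positive rate returns to 4–6% and the mean error is within 0.04. Without adjustment the half-width is already about 1.0–1.5. If severity does not moderate response, the false effect is zero.

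**4. The reverse direction.** If only location matters, with effect 1.0, mild children have none of it and severe children have it in 30–70% of cases. The false mild–severe gap is then 0.3–0.7. Adjusting location tests for severity does nothing for this.

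**The case for a change.** The best argument for a change is that it would be cheap. One sentence would fix the missing level and another would put severity into the location model. Physician input settles single cases but is not a rule, so readers cannot reconstruct the groups. The overlap comes from the index itself, nothing in the plan guards against an unadjusted location test, and adjustment does restore the error rate.

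Part of this stands. The level is not written down, and an unadjusted location contrast would be open to confounding by severity. The rest weakens on inspection:

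- The competing readings of the missing level are not equal. Moderate ignores the sentence demanding further evidence. Not rated sits badly with criteria that require a mild, moderate or severe rating. A child who fails the test for at least moderate is most naturally mild.
- The plan specifies ANCOVA on brain injury variables, in the plural. It does not say that location will be tested without severity; that model is simply not spelled out.
- Severity and location are not inseparable. Location still varies within the moderate and severe groups, which is why the adjusted estimate is close to unbiased.
- Mandatory adjustment buys that at a price. Half-widths reach almost 1.9 SD, and in one setting about half the simulated trials had too few location-positive children to count. The severity comparison would keep its own version of the problem.

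**Conclusion.** No change follows. The missing level is a gap that the investigators and the specialist physician can fill sensibly, and project staff stay blinded to treatment order until the last follow-up interview. The choice would typically move the mild–moderate contrast by 0.13–0.26 SD (mild or not rated) or 0.28–0.49 SD (mild or moderate), against a mild–severe half-width of 1.14–1.55 SD.

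The overlap of severity with CT location is genuine. Its harm requires a strong severity gradient (1.0 SD assumed here) together with an unadjusted test that the plan does not call for. Under those conditions the false effect is 0.19–0.62 SD, and the error rate runs from about nominal to 19%, depending on the split. Whether to adjust with about 20 children is a fair trade-off between bias and precision. Three-group power for a 1.0 SD mild–severe gap is only 18–29%, so these results are exploratory either way, in a study that its Stopping Rules paragraph describes as a pilot.

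The reference to mediation is a slip of wording. The personality entry would either be met from the behavioral and emotional scales already collected, though no text says so, or not be run. The primary LDX-versus-placebo paired t-tests use none of these variables. All sizes rest on the assumed splits and CT shares shown above; the logic of the rule does not.

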This will be the first study to examine the use of LDX in treating attention deficits in children with TBI. It will be the most rigorous study to date examining stimulant medication treatment of any kind with this population. It is predicted that, as in the initial trial with adults, positive treatment effects will be found on a spectrum of outcomes having to do with attention and the various areas affected by it. Safety and tolerability will be carefully examined for the use of LDX in this clinical application. Also, as was done in the initial trial, treatment outcomes will be examined in terms of potentially moderating effects having to do with a broad range of pre-treatment subject characteristics and injury variables, including the pattern and severity of TBI, age of injury, as well as certain cognitive and behavioral factors at baseline. In our previous trial with adults, subjects with greater functional limitations pretreatment (lower IQ, problems with executive functioning) showed better treatment response with LDX on some outcome indices.

Overall, this will be a novel study examining the treatment of TBI-related attention deficits in children. The primary aim is to conduct a sound clinical trial examining outcomes with LDX as the treatment, but the objectives of the study go beyond that. More broadly, the aim is to gain further insights into the nature of attention deficits and their treatment in children with TBI. Based on the existing research, there are likely to be unique relationships involving children with TBI versus idiopathic ADHD. The hope is that this trial will help inform and guide further investigations in this area.

Methods

Subject Selection

The subject sample is to consist of approximately 20 children diagnosed with TBI-related attention deficits. The specific selection criteria are noted below.

Inclusion Criteria:

- Males and females ages 6 to 16
- Traumatic brain injury rated as mild/moderate/severe (based on *Glasgow Coma Scale*, estimated posttraumatic amnesia, indications of intracranial injury on CT scan, etc.)
- Sustained 2-36 months earlier
- Considered to be neurologically stable (absence of post-acute symptoms of confusion, disorientation, etc.)
- Persistent (> 2 months) problems with focused or sustained attention
- Problems with attention/concentration rated as among the most prominent cognitive changes
- Accompanying features may include diminished arousal/speed/stamina and/or hyperactivity/impulsivity symptoms.

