As in the initial study, this will be a randomized, double-blind, placebo-controlled, crossover trial. Following enrollment, each case will be randomly assigned to one of two treatment sequences, alternating on whether stimulant treatment or placebo comes first. Each phase will be 6 weeks long, resulting in a total duration of 12 weeks. Comprehensive neurobehavioral assessments will occur at baseline, 6 weeks, and 12 weeks. More streamlined behavior ratings along with safety monitoring and medication/placebo dispensing (see below) will be done during weekly visits.

Medication Trial

Source: Medication will be supplied by Shire Pharmaceuticals. The Vanderbilt Investigational Drug Service (IDS) will repackage the active medication to provide placebo and drug capsules identical in size (the smallest available) and appearance that will remain the same throughout the trial. The IDS will perform medication blinding and distribution to the study nurse.

Protocol: Enrolled children will enter a pre-determined randomization scheme as designed by the IDS. They will receive LDX (Vyvanse) 20-70 mg or placebo for 6 weeks. At the end of six weeks (day 43 after treatment initiation) each subject will switch from the current agent (drug or placebo) to the alternative (drug or placebo). Based on manufacturer's guidelines and clinical experience, no taper or washout period is deemed necessary either in switching from active drug to placebo or at termination of treatment.

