Titration: All subjects in the LDX treatment phase of the protocol will initiate dosing at 20 mg po on study day 1 and continue on that for week 1. (The usual starting dose is 30 mg for children 6 years of age and older with idiopathic ADHD, but it was decided to begin with a more conservative starting point given the off-label use in the present trial.) If tolerated without indication of medication sensitivity (such as mild increases in anxiety, insomnia, weight loss, etc.), all subjects will be increased to 30 mg at week 2. Thereafter, if tolerated, they will be increased to 50 mg at week 3 and again at week 4 to a maximum dosage of 70 mg. Increments will be scaled back to a rate of 10 mg weekly at any point if there are concerns about possible medication sensitivity. Subjects will remain at the maximum tolerated dose for the remainder of the trial unless they meet safety endpoints for withdrawal (see below) or they request to exit the study. Cases with certain medical conditions (e.g., those with known or suspected renal dysfunction) will not be advanced to a daily dose beyond 50 mg. Weekly parent/subject ratings on the Clinical Global Impression-Severity (CGI-S) Scale (a standard measure of subjective treatment response used in clinical drug trials) will be taken into consideration in making dosing adjustments. If a subject tolerates lower dosing(s) but reports tolerability problems after a dose increase, the dose will be titrated downward to the prior tolerated dose level. Dosing adjustments may occur up to the start of week 6 if necessary. The same titration schedule and guidelines will apply during both the drug and placebo phases of the trial.

Safety Endpoints: These will serve as withdrawal criteria if met or exceeded. They include both psychiatric AEs (new onset suicidality, psychosis, or other serious reaction requiring psychiatric intervention) as well as medical AEs (above the designated safety cutoff with respect

to hypertension, tachycardia, etc., or any other evidence suggestive of a severe adverse effect of the study drug).

De-blinding: Because placebo and active drug for all dosages will be packaged in opaque capsules of fixed size by the IDS, the study investigators and subjects will be blinded to drug/placebo status. IDS will provide this information to the PI or other medical personnel in the case of a patient medical emergency. If blinding is broken for this reason, the subject must exit the study.

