Safety Assessment: Patients will undergo weekly (+/-3 days) monitoring by the project nurse. Safety monitoring will include assessment of any self- or parent-reported adverse events (AEs), assessments of blood pressure, heart rate and weight, as well as psychiatric symptom assessment including suicidality.

Safety Endpoints: Safety endpoints will serve as withdrawal criteria if met or exceeded. They include:

Psychiatric

- New onset suicidality
- Mania
- Psychosis
- Other acute and serious reaction requiring immediate psychiatric intervention

Medical

- Hypertension (SBP and/or DBP greater than 95th percentile for child's age on two or more consecutive readings separated by at least 10 minutes)

- Tachycardia (symptomatic tachycardia or sustained heart rate greater than 150% of resting baseline heart rate on two or more consecutive readings separated by at least 10 minutes)
- Chest pain (judged by the study physician to be of likely cardiac origin)
- Other evidence suggestive of severe adverse effect of study drug
- Significant weight loss (> 10% compared to baseline level, and which persists despite downward titration)
- Pregnancy
- Introduction of a medication by subject's medical provider if that medication is on the list of excluded medications

Parents will be provided with contact information and instructions of what to do if questions or concerns regarding possible problems or safety issues should arise. Adverse medical events will be brought to the attention of the project physician who will initiate appropriate follow-up action as needed. All adverse events will also be communicated immediately to the PI (see below). Withdrawn patients and their parents will be provided with an explanation for their withdrawal and will be referred to an appropriate care provider for clinical management as needed.

Safety Reports: All adverse events (AEs) will be communicated immediately to the PI for follow-up review. Severe adverse events (SAEs) will be reported to the PI, IRB and study sponsor according to IRB guidelines.

The following are types of events that require reporting to the IRB. If the event does not fit the categories, the event is not reportable to the IRB; however, it may be reportable to the sponsor.

- a) Any event that requires prompt reporting to the sponsor, in accordance with the protocol (e.g., serious adverse events);
- b) Accidental or unintentional change to the IRB-approved protocol that involves risks or has the potential to recur;

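### Insomnia and appetite loss are to be compared between LDX and placebo without a fixed item list, severity grade or baseline rating, so the comparison may lose sensitivity

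*Combined protocol and SAP*

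**What the plan says.** The closing paragraph of Data Analyses commits to an LDX-versus-placebo comparison, from the weekly visits, of blood pressure, heart rate and "side effects (insomnia, decreased appetite or weight loss, etc.) or significant adverse events, if any". It names no case definition, grade or test for side effects. The general rules of that section are "A p value equal to, or less than, 0.05 will be considered statistically significant" and "All tests will be two-tailed".

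Safety Monitoring (Safety Assessment) describes the weekly nurse visit. It comprises "assessment of any self- or parent-reported adverse events (AEs"), together with "assessments of blood pressure, heart rate and weight, as well as psychiatric symptom assessment including suicidality". Weight and the psychiatric state are therefore assessed directly each week. Sleep and appetite are not on that list and can enter only as reported adverse events.

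Medication Trial (Titration) also refers to one of these symptoms. The first dose increase is conditional: "If tolerated without indication of medication sensitivity (such as mild increases in anxiety, insomnia, weight loss, etc".). Weekly CGI-S ratings are considered in dosing as well.

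Baseline references do exist for some items. The safety endpoints define weight loss and tachycardia relative to baseline, and Neurobehavioral Assessments schedules an anxiety scale at baseline, 6 weeks and 12 weeks. No baseline rating of sleep or appetite is named.

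**The concern.** Two named symptoms are to be compared between treatments, and one of them is also a titration sign worded as an increase. The protocol does not say what is asked, how severity is graded, or what an increase in insomnia is measured against. If questioning varies between visits or families, some events will not be recorded. If a child already slept or ate poorly before the first capsule, the complaint may be listed in both phases and contribute nothing to the contrast.

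The Introduction promises that safety and tolerability will be examined carefully. There is no data safety monitoring board and there are no stopping rules, so the weekly visit is the only source for this comparison. With about 20 children, a few missed events can decide whether a difference is seen, and a null result would be hard to interpret. Symptoms not asked about during the trial cannot be recovered afterwards.

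**Working it through.** **Is the gap filled elsewhere?** As the protocol describes them, the other instruments do not fill it:

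- The CGI-S is presented as a measure of subjective treatment response.
- The weekly Conners-3 short form rates ADHD symptoms and related areas.
- The Post-TBI Symptom Questionnaire is a screening form on mental functioning.
- The Child Behavior Checklist and the depression and anxiety scales are given at baseline, 6 weeks and 12 weeks only. None is named in the safety analysis. Their item content is not in the documents, so I draw nothing from it.

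**What could incomplete capture cost?** The plan states no power or event rate for side effects, so there is no figure to reproduce.

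Inputs from the protocol: "The subject sample is to consist of approximately 20 children diagnosed with TBI-related attention deficits" (N = 20); two-sided alpha 0.05; a crossover in which "each case will be randomly assigned to one of two treatment sequences, alternating on whether stimulant treatment or placebo comes first", so each child supplies both phases.

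Assumptions: true rates of 50% on LDX and 10% on placebo; the same capture fraction f in both phases; an exact two-sided McNemar test (the plan names none); a latent (bivariate normal) within-child correlation of 0.3.

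Formulas:

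- Recorded rates: a = 0.50f and b = 0.10f.
- Probability recorded in both phases, p11: the bivariate normal probability with margins a and b and correlation 0.3.
- Discordant probabilities: p10 = a − p11 (LDX only) and p01 = b − p11 (placebo only).
- Power: the sum, over the number m of discordant children, of Bin(m; 20, p10 + p01) times the probability that the split of m gives p ≤ 0.05 in favour of more events on LDX.

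The p-value for m children all in one direction is 2 × 0.5^m. For m = 5 it is 0.0625 and for m = 6 it is 0.031. At least six discordant children are therefore needed, and with exactly six all must point the same way.

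| Capture f | a, b | p10, p01 | Risk difference | Risk ratio | Power |
|---|---|---|---|---|---|
| 1.00 | 0.500, 0.100 | 0.429, 0.029 | 40 points | 5 | 0.76 |
| 0.90 | 0.450, 0.090 | 0.390, 0.030 | 36 points | 5 | 0.67 |
| 0.75 | 0.375, 0.075 | 0.330, 0.030 | 30 points | 5 | 0.50 |
| 0.50 | 0.250, 0.050 | 0.226, 0.026 | 20 points | 5 | 0.20 |

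Relative to full capture, the loss of power is (0.76 − 0.50)/0.76 = 34% at three-quarters capture and (0.76 − 0.20)/0.76 = 74% at half capture.

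Sensitivity of power at f = 0.90, 0.75 and 0.50:

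- 40% versus 10%, correlation 0.3: 0.39, 0.27, 0.09.
- 60% versus 15%, correlation 0.3: 0.74, 0.58, 0.27.
- 50% versus 10%, independent phases: 0.61, 0.46, 0.20 (0.69 with full capture).

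**What could pre-existing complaints cost?** Suppose a fraction s of children have the symptom beforehand and are scored positive in both phases. With independent phases and full capture, the discordant probabilities become (1 − s) × 0.50 × 0.90 = 0.45(1 − s) and (1 − s) × 0.10 × 0.50 = 0.05(1 − s). Power is 0.69 at s = 0, 0.53 at s = 0.2 and 0.32 at s = 0.4. For 40% versus 10% it is 0.44, 0.30 and 0.15. Scoring change from baseline separates old complaints from new or worse ones.

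**The case against.** A reader might infer that side effects are merely volunteered. The text does not say so. It names the informant, not the manner of questioning, and staff who must judge insomnia before a dose step have a reason to ask about it. That stands: under-recording is a risk, not a documented fact. What remains is that nothing requires the same questions at each visit.

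A reader might also infer that there is no baseline at all, or that dosing rests on reports alone. Neither is supported. Weight, heart rate and anxiety have baseline values, a psychiatric symptom assessment is made weekly, and CGI-S and measured weight are also available to dosing. The baseline gap is confined to sleep and appetite.

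Nor does the gap bias the result toward either treatment by itself. Each child also has a placebo phase under the same blinded monitoring, so equal under-capture preserves the ratio. It still reduces the difference and the power.

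The capture model uses one chance per phase, whereas visits are weekly. With independent 50% capture per visit, a symptom present at three visits would be recorded at least once with probability 1 − 0.5³ = 0.875. Independence is optimistic, since a family that does not mention a symptom once may not mention it later, but the point makes the 50% row an unfavourable case.

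Finally, complete capture does not make this an adequately powered safety test. At 40% versus 10% with independent phases, power is only 0.44. The main limit is the sample size of a self-described pilot. That is correct, and it is a reason not to lose events that could be recorded cheaply.

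**Conclusion.** The specification gap is real and narrow. Insomnia and decreased appetite are to be compared between treatments, and insomnia is mentioned at titration, but neither has a fixed item, grade or baseline rating. Incomplete capture and carried-over complaints are possible consequences.

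Under the assumed 50% versus 10%, power falls from about 0.76 with full capture to 0.67, 0.50 and 0.20 at 90%, 75% and 50% capture. The stronger statement that most of the power will be lost holds only if about half of events or more go unrecorded; at three-quarters capture about a third is lost. Event rates, capture rates, the correlation and the choice of McNemar are all assumptions. Blood pressure, heart rate and weight are measured directly and are not affected.

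This is a worthwhile, inexpensive improvement to the safety comparison. It is not a flaw that undermines the trial.

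**What to change.** In Safety Assessment, add one fixed side-effect checklist, including at least sleep and appetite, with each item graded 0 to 3. Give it once at baseline and in identical form at every weekly nurse visit in both phases. Keep open-ended adverse-event reporting alongside it.

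In Data Analyses, state that for each item the proportion of children in whom it is newly present or worse than baseline will be compared within child, LDX versus placebo, and name the paired test (for example exact McNemar).

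No change to the dosing rule is proposed.

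The cost is a one-page form at visits already held and a sentence in the analysis section, with no extra staff. The downside is that more minor events will be recorded in both phases. Power will still be limited by about 20 children, so a non-significant difference should not be read as evidence of no harm.
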